1. OBJECTIVES

1.1 Study Design

A Simon 2-stage design will be implemented for each disease cohort. Patients will be treated with two-week lead-in, followed by a 6-week combined targeted therapy (TT) and pembrolizumab, followed by maintenance single-agent pembrolizumab in all patients with RECIST defined stable disease (SD), partial response (PR), and complete response (CR). TT will be resumed if patients develop symptomatic or radiographic evidence of progression. If patients do not develop evidence of progressive disease (PD), then they will continue maintenance single-agent pembrolizumab for up to two years. In each cohort, patients will be accrued to first stage of the Simon design. If a prespecified number of patients maintain SD/PR/CR off TT but on pembrolizumab, then the second stage of the two-stage design will be opened. (Please see details in statistical section) Biopsies will be performed on all patients enrolled to the first stage of the Simon two-stage for each cohort. These will be obtained at baseline and after the two-week lead-in. A third biopsy obtained after the completion of induction therapy will be obtained if feasible. An optional biopsy at time of disease progression will also be performed.

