A Simon 2-stage design will be implemented for two disease cohorts, BRAF^{V600} mutant and BRAF^{V600} wild-type unresectable Stage III or Stage IV melanoma. Patients will be treated with a two-week lead-in of MTT, followed by a 6-week course of combined MTT and pembrolizumab (at dose of 200 mg IV every three weeks), followed by maintenance single-agent pembrolizumab in all patients with RECIST defined stable disease (SD), partial response (PR), and complete response (CR). *MTT only will be resumed* if patients develop symptomatic or radiographic evidence of progression. If patients do not develop evidence of progressive disease (PD), then they will continue maintenance single-agent

CONFIDENTIAL

This document is confidential. Do not disclose or use except as authorized.

pembrolizumab for up to two years; at which time treatment will be discontinued. In each cohort, patients will be accrued to first stage of the Simon design. If a pre-specified number of patients maintain SD/PR/CR off MTT but on pembrolizumab at the 24-week time point, then the second stage of the two-stage design will be opened. (Please see details in statistical section). Biopsies will be performed on all patients enrolled to the first stage of the Simon two-stage for each cohort. These will be obtained at baseline, after the two-week lead-in, and after the completion of induction therapy if feasible. An optional biopsy at the time of disease progression will also be performed.

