5.5 Criteria for Taking a Participant off Protocol Therapy

Duration of therapy will depend on individual response, evidence of disease progression and tolerance. In the absence of treatment delays due to adverse events, treatment may continue until one of the following criteria applies:

- Completion of two years of pembrolizumab therapy
- Disease progression, unless patient meets criteria for treatment beyond progression in Section 5.5.1
- Intercurrent illness that prevents further administration of treatment,

CONFIDENTIAL

This document is confidential. Do not disclose or use except as authorized.

- Unacceptable adverse event(s),
- Participant demonstrates an inability or unwillingness to comply with the oral medication regimen and/or documentation requirements
- Participant decides to withdraw from the study, or
- General or specific changes in the participant's condition render the participant unacceptable for further treatment in the opinion of the treating investigator.

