5.5.1.3 Pembrolizumab single-agent

Patients who develop progression of disease on the pembrolizumab single-agent phase will be allowed to be treated beyond progression as long as the following criteria are met:

- A. Absence of signs and symptoms (including worsening of laboratory values) indicating disease progression.
- B. No decline in ECOG performance status.
- C. Absence of rapid progression of disease.
- D. Absence of progressive tumor at critical anatomical sites (e.g., cord compression) requiring urgent alternative medical intervention.

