5.6 Duration of Follow Up

If treatment is discontinued for completion of two years of pembrolizumab, or for disease progression, or for withdrawal of consent, participants will be followed for adverse events. All adverse events encountered from time of the first dose of study treatment up until 90 days after the last dose of study treatment will be followed until one of the following occurs:

- The event resolves,
- The participating investigator assesses the event as stable,
- The participating investigator determines the event to be irreversible,
- The participant is lost to follow-up,
- The participant dies.

If the subject is not seen in clinic after the off-study visit, required Adverse Event details must be collected over the phone.

CONFIDENTIAL

This document is confidential. Do not disclose or use except as authorized.

If treatment is discontinued for a reason other than disease progression, study discontinuation, or withdrawal of consent, participants will be seen every 12 weeks (+/- 2 weeks) for imaging until progressive disease or death, whichever comes first. If there are any adverse events that have not resolved, or been assessed by the participating investigator as stable or irreversible at the time of progressive disease, the participant will be followed until the adverse events resolve, or are assessed by the participating investigator as stable or irreversible.

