5.7 Criteria for Taking a Participant Off Study

Participants will be removed from study when any of the criteria listed in Section 5.6 applies. The reason for study removal and the date the participant was removed must be documented in the study-specific case report form (CRF). Alternative care options will be discussed with the participant.

In the event of unusual or life-threatening complications, participating investigators must immediately notify the Principal Investigator, [name] at [contact].

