7.5 Monitoring of Adverse Events and Period of Observation

All adverse events, both serious and non-serious, and deaths that are experienced by participants will be collected from the time of the first dose of study treatment up until 90 days after the last dose study treatment, or until death if death occurs first. The presence and resolution of AEs and SAEs (with dates) should be documented on the appropriate case report form and recorded in the participant's medical record to facilitate source data verification.

For some SAEs, the Overall PI or designee may follow-up by telephone, fax, and/or monitoring visit to obtain additional case details deemed necessary to appropriately evaluate the SAE report (e.g., hospital discharge summary, consultant report, or autopsy report).

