10. STUDY CALENDAR

Baseline evaluations are to be conducted within 2-weeks prior to start of protocol therapy. Scans must be done \leq 4 weeks prior to the start of therapy. All assessments must be performed prior to administration of any study medication. On days when TSH is required, TSH is not required to be resulted prior to administration of study medication. All study assessments and medications should be administered within \pm 3 days of the protocol-specified date, unless otherwise noted. Laboratory values do not need to re-meet eligibility criteria on Week 1, Day 1.

CONFIDENTIAL

This document is confidential. Do not disclose or use except as authorized.

BRAF ^j	X			X	X	X	X	X	X	X	X	X ⁱ	
PBMC ^k	X			X		X	(X)						
Tumor Biopsies ^k	X			X		X	(X)						
Rash Prophylaxis ^q		X ^q	X ^q	X ^q	X ^q								

- a. MAPK targeted therapy (MTT): In cohort 1, participants will be treated with the combination of dabrafenib and trametinib. In cohort 2, participants will be treated with trametinib. MTT will commence week 1, day 1 and be given continuously (except in the setting of toxicity) for two weeks in the lead-in phase and then 6-weeks in combination with pembrolizumab. Only if patients develop symptomatic or radiographic progression at anytime AFTER initial MTT-phase completion, then MTT may be resumed at a previously tolerated dose in combination with ongoing pembrolizumab.
- b. Participants will be seen on day 1 (+/-3 days) of week 1, week 3, and then every three weeks while remaining on therapy. If treatment is discontinued for a reason other than disease progression, study discontinuation, or withdrawal of consent, patients will be seen every 12 weeks (+/- 2 weeks).
- c. Dermatological examination done at screening, and within 1 week prior to dosing on week 9. A full-body skin examination and removal of pre-existing calluses and keratotic skin is recommended prior to initiation of study treatment (See Table 6-4).
- d. Ophthalmological examination done at screening and within 1 week prior to treatment on week 9. For Grade 2 visual changes or greater, an exam must occur within 24 hours of onset (or study team knowledge of the event). Consult ophthalmologist any time when patient reports visual disturbance. If there is visual loss or significant visual changes, consult ophthalmologist immediately (within 24 hours)
- e. Single EKG will be collected at screening and repeated on day 1 of weeks 3 and 6 in cohort 1.

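### No vital-status follow-up is scheduled after stopping for progression, so one-year OS is likely to be biased upward

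*Combined protocol and SAP*

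**What the plan says.** **Stopping at progression.** Section 5.5 lists as a reason to end protocol therapy: "Disease progression, unless patient meets criteria for treatment beyond progression in Section 5.5.1". For the single-agent pembrolizumab phase, criterion A in 5.5.1.3 is "Absence of signs and symptoms (including worsening of laboratory values) indicating disease progression"; B to D concern performance status, speed of progression and critical sites.

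**Follow-up after stopping for progression.** Section 5.6 groups progression with completion of two years of pembrolizumab and withdrawal of consent: "or for disease progression, or for withdrawal of consent, participants will be followed for adverse events". The 12-weekly visits in 5.6 and in calendar notes m and r are for patients who stop for other reasons. Section 5.7 adds: "Participants will be removed from study when any of the criteria listed in Section 5.6 applies".

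**Collection of deaths.** Section 7.5 sets the window: "deaths that are experienced by participants will be collected from the time of the first dose of study treatment up until 90 days". The count of 90 days starts at the final dose.

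**What the analysis needs.** Section 1.3.1 names one-year OS as a secondary objective. Section 13.1.1 measures OS from the first dose of targeted therapy to death from any cause and censors patients without a documented death at their last vital-status assessment. Section 13.4 gives Kaplan-Meier estimates, including one-year OS. No section of the text as read says when vital status is assessed once a patient has stopped for progression.

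**Resumed targeted therapy.** Section 1.1 says "TT will be resumed if patients develop symptomatic or radiographic evidence of progression", and 5.1 gives the same trigger, "if patients develop symptomatic or radiographic evidence of progression". Calendar note a is permissive: "then MTT may be resumed at a previously tolerated dose in combination with ongoing pembrolizumab".

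**The concern.** Death collection is tied to the last dose, but the endpoint is tied to a fixed time from the first dose. A patient who progresses early and stops leaves the 90-day window well before one year, and no later contact is scheduled.

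The censoring is not neutral. These patients stop being observed because their disease has progressed, which is when their risk of death rises. Kaplan-Meier treats them as having the same future risk as patients still under observation, most of whom have not progressed. The one-year estimate is therefore pushed upward.

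With 25 patients per cohort, or 14 if a cohort stops after stage 1, a few missed deaths are enough to alter the reported figure. Single-arm survival estimates of this kind are usually read against historical data, so an upward error flatters the regimen.

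**Working it through.** The plan states no precision or power for one-year OS, so there is no figure of its own to reproduce on this point. As a check on the design, the Simon figures do reproduce by exact binomial calculation: probability of early stopping under the null 0.788 (stated 0.79) and power 0.862 (stated 86%). They do not depend on this point.

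**1. How far death collection reaches for a patient who stops**

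Inputs: OS origin at the first MTT dose in week 1 (13.1.1); pembrolizumab every three weeks from week 3 (5.3.1, Section 10); scans before W15, W21 and W27 and then 12-weekly (11.1); deaths collected to 90 days after last dose (7.5). 90 days = 12.86 weeks; one year = 52.18 weeks.

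End of collection, in weeks from first dose = (last-dose week − 1) + 12.86.

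| Progression at scan for | Last dose | Collection ends (weeks) | Short of one year by (weeks) |
|---|---|---|---|
| W15 | W12 | 11 + 12.86 = 23.9 | 28.3 |
| W21 | W18 | 17 + 12.86 = 29.9 | 22.3 |
| W27 | W24 | 23 + 12.86 = 35.9 | 16.3 |
| W39 | W36 | 35 + 12.86 = 47.9 | 4.3 |

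Break-even last dose: 52.18 − 12.86 + 1 = study week 40.3. Any earlier last dose falls short.

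**2. What resuming MTT does**

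Resumption only moves the last dose. For MTT resumed at W15 (14 weeks elapsed), the time on MTT needed to reach one year is 52.18 − 12.86 − 14 = 25.3 weeks, or 5.8 months (4.348 weeks per month). As a rough guide, take the first-exposure median PFS figures in the background as time on resumed drug; re-treatment may be shorter.

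- Cohort 1, dabrafenib plus trametinib, 9.4 months (2.2.2.4): 14 + 9.4 × 4.348 + 12.86 = 67.7 weeks, past one year.
- Cohort 2, trametinib alone, 4.8 months (2.2.3.2, in BRAF-mutant patients): 14 + 4.8 × 4.348 + 12.86 = 47.7 weeks, still short.

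The gap therefore remains in part even if every eligible patient resumes MTT.

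**3. Size of the effect**

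One missed death moves a cohort's one-year OS by up to 1/25 = 4.0 points, or 1/14 = 7.1 points after a stage 1 stop.

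For the net bias, a Kaplan-Meier simulation was run with n = 25 and 4000 runs. All of these inputs are assumed: 2 to 6 patients stop for progression at W15, W21 or W27 at random, survival after progression is exponential, and the others have 90% one-year survival. Full follow-up is compared with censoring 90 days after last dose.

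| Patients stopping | Median survival after progression | One-year OS, full follow-up | One-year OS, 90-day rule | Bias (points) |
|---|---|---|---|---|
| 2 | 52 weeks | 0.881 | 0.895 | +1.4 |
| 4 | 39 weeks | 0.848 | 0.884 | +3.7 |
| 6 | 26 weeks | 0.786 | 0.857 | +7.1 |

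A second model let progression occur continuously, with a share of progressors between 25% and 100% stopping at progression. It gave about 1 to 13 points; the top of that range needs every progressor to stop and a six-month median thereafter. Both models give an upward bias; the size depends on the inputs.

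**4. Endpoints not affected**

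A patient who has progressed by the week-24 scan has no clinical benefit whatever follow-up comes after, so CBR and the stage decisions stand. PFS ends at first progression, before the gap opens.

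**The case against.** **OS has its own censoring rule.** Section 7.5 is an adverse-event section, while 13.1.1 censors at last vital-status assessment and 11.1.6 at the date last known alive. Section 5.4.2 also mentions a post-treatment follow-up phase. On this view later deaths would be picked up anyway, and many centres would do so from their records. What stands: the documents do not forbid it, so censoring at 24 to 36 weeks is what follows if only the written rules are applied. But nothing in the text as read requires or schedules the contact, and 5.7 removes the patient from study.

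**Progressors generally stay on trial.** Section 5.5.1 says so, and 5.1 places resumed MTT within the treatment regimen. This reduces the number of patients affected. It does not remove the gap, because collection still ends 90 days after the last dose of whatever is given.

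**The calendar grid.** Most of it is missing from the text as read, so a survival row cannot be excluded. The calendar notes mention none.

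**A stronger inference to avoid.** A reader might conclude that the clash between criterion A and the resumption rule in 1.1, 5.1 and note a is what determines one-year OS. The documents do not support that. Section 5.5.1.2 applies the same four criteria expressly to single-agent pembrolizumab, so they can be read as governing pembrolizumab alone. Resumption only shifts the last dose, both readings reach one year once that dose is at about week 40 or later, and both can fall short in cohort 2. Asymptomatic progressors who stop face the same gap.

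**Conclusion.** The point holds as a follow-up gap: 5.6, 5.7 and 7.5 do not supply the data that 13.1.1 and 13.4 need. Followed as written, the plan stops collecting deaths 4 to 28 weeks before one year for patients whose last dose falls between W36 and W12. Because they stop for progression, the censoring is informative and one-year OS is likely biased upward.

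The week counts follow from the documents. The bias of about 1 to 7 points is an illustration that rests wholly on assumed numbers of patients, post-progression survival and survival in the rest. The direction rests on two assumptions: that risk of death rises after progression, and that no vital status is obtained beyond the 90-day window.

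The unclear status of MTT resumed for symptomatic progression is a secondary contributor, because it changes the last-dose date. One-year OS is a descriptive secondary endpoint, and CBR, PFS and the Simon decision are untouched. This is worth correcting, but it does not threaten the trial's main conclusion.

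**What to change.** Two additions:

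- **Section 5.6:** 'Vital status is recorded every 12 weeks until death or final analysis (at least 12 months from first dose) for all participants, whatever the reason for stopping treatment and whatever therapy follows, unless consent to follow-up is withdrawn.'
- **Section 5.7:** 'Removal from study for progression does not end vital-status follow-up.'

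With these, deaths are sought to one year whether or not MTT is resumed, so the ambiguity about resumption no longer matters for OS. No change to 5.5.1.3 is needed for this purpose. In particular, wording that leaves continued pembrolizumab to the investigator when criteria B to D fail should not be added, since it would relax safety conditions.

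The cost is one phone or record check every 12 weeks for each patient off therapy. For a W15 progressor last dosed at W12, 28.3 / 12 = 2.4, so about three checks reach one year. Sample size, treatment, scans and analyses do not change. If the full calendar grid already has a survival row, it should be cross-referenced in 5.6 and 5.7.

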5.5.1.4 Follow up after discontinuation of pembrolizumab in setting of a CR

Discontinuation of treatment may be considered for subjects who have attained a confirmed CR that have been treated for at least 24 weeks with pembrolizumab and had at least two treatments with pembrolizumab beyond the date when the initial CR was declared. Subjects who discontinue treatment and then experience radiographic disease progression may be eligible for up to one year of additional treatment with single-agent pembrolizumab at the discretion of the investigator if no cancer treatment was administered since the last dose of pembrolizumab, the subject meets the safety parameters listed in the Inclusion/Exclusion criteria, and the trial is open. Subjects will resume therapy at the same dose and schedule at the time of initial discontinuation.

5.6 Duration of Follow Up

If treatment is discontinued for completion of two years of pembrolizumab, or for disease progression, or for withdrawal of consent, participants will be followed for adverse events. All adverse events encountered from time of the first dose of study treatment up until 90 days after the last dose of study treatment will be followed until one of the following occurs:

- The event resolves,
- The participating investigator assesses the event as stable,
- The participating investigator determines the event to be irreversible,
- The participant is lost to follow-up,
- The participant dies.

If the subject is not seen in clinic after the off-study visit, required Adverse Event details must be collected over the phone.

CONFIDENTIAL

This document is confidential. Do not disclose or use except as authorized.

If treatment is discontinued for a reason other than disease progression, study discontinuation, or withdrawal of consent, participants will be seen every 12 weeks (+/- 2 weeks) for imaging until progressive disease or death, whichever comes first. If there are any adverse events that have not resolved, or been assessed by the participating investigator as stable or irreversible at the time of progressive disease, the participant will be followed until the adverse events resolve, or are assessed by the participating investigator as stable or irreversible.

5.7 Criteria for Taking a Participant Off Study

Participants will be removed from study when any of the criteria listed in Section 5.6 applies. The reason for study removal and the date the participant was removed must be documented in the study-specific case report form (CRF). Alternative care options will be discussed with the participant.

In the event of unusual or life-threatening complications, participating investigators must immediately notify the Principal Investigator, [name] at [contact].

5.8 Contraception

Pembrolizumab may have adverse effects on a fetus in utero. Furthermore, it is not known if pembrolizumab has transient adverse effects on the composition of sperm. For this trial, male subjects will be considered to be of non-reproductive potential if they have azoospermia (whether due to having had a vasectomy or due to an underlying medical condition).

Female subjects will be considered of non-reproductive potential if they are either:

(1) Postmenopausal (defined as at least 12 months with no menses without an alternative medical cause; in women < 45 years of age a high follicle stimulating hormone (FSH) level in the postmenopausal range may be used to confirm a post-menopausal state in women not using hormonal contraception or hormonal replacement therapy. In the absence of 12 months of amenorrhea, a single FSH measurement is insufficient.);

OR

(2) Have had a hysterectomy and/or bilateral oophorectomy, bilateral salpingectomy or bilateral tubal ligation/occlusion, at least 6 weeks prior to screening;

OR

CONFIDENTIAL

This document is confidential. Do not disclose or use except as authorized.

(3) Has a congenital or acquired condition that prevents childbearing. Female and male subjects of reproductive potential must agree to avoid becoming pregnant or impregnating a partner, respectively, while receiving study drug and for 120 days after the last dose of study drug by complying with one of the following:

Female subjects of childbearing potential and male subjects with partners of childbearing potential must:

(1) Practice abstinence† from heterosexual activity;

OR

(2) Use (or have their partner use) acceptable contraception during heterosexual activity.

Acceptable methods of contraception are:

Single method (one of the following is acceptable):

- Intrauterine device (IUD)
- Vasectomy of a female subject's male partner
- Contraceptive rod implanted into the skin

Combination method (requires use of two of the following):

- Diaphragm with spermicide (cannot be used in conjunction with cervical cap/spermicide)
- Cervical cap with spermicide (nulliparous women only)
- Contraceptive sponge (nulliparous women only)
- Male condom or female condom (cannot be used together)
- Hormonal contraceptive: oral contraceptive pill (estrogen/progestin pill or progestin-only pill), contraceptive skin patch, vaginal contraceptive ring, or subcutaneous contraceptive injection

†Abstinence (relative to heterosexual activity) can be used as the sole method of contraception if it is consistently employed as the subject's preferred and usual lifestyle and if considered acceptable by local regulatory agencies and ERCs/IRBs. Periodic abstinence (e.g., calendar, ovulation, sympto-thermal, post-ovulation methods, etc.) and withdrawal are not acceptable methods of contraception.

‡If a contraceptive method listed above is restricted by local regulations/guidelines, then it does not qualify as an acceptable method of contraception for subjects participating at sites in this country/region.

Subjects should be informed that taking the study medication may involve

CONFIDENTIAL

This document is confidential. Do not disclose or use except as authorized.

unknown risks to the fetus (unborn baby) if pregnancy were to occur during the study. In order to participate in the study subjects of childbearing potential must adhere to the contraception requirement (described above) from the day of study medication initiation (or 14 days prior to the initiation of study medication for oral contraception) throughout the study period up to 120 days after the last dose of trial therapy. If there is any question that a subject of childbearing potential will not reliably comply with the requirements for contraception, that subject should not be entered into the study.

